Title page Section 3 Investigators and other study participants	Medical Expert contact information update	Contact information for Medical expert has been updated
Synopsis Section 5.1.1 Inclusion criteria	Change in the definition of MTP from 3 injections to 3 Exposure days	Clarification that MTPs do not have more than 3 EDs with any FVIII concentrate, as number of injections and exposure days are not necessarily identical.
Section 4 study design	Addition that screening can continue whilst first cohort completes 20 ED	
Protocol Amd 7 introduced a staggered enrollment and treatment approach to limit the entry of patients into the study until safety data related to inhibitor development during the first 20 EDs could be assessed in the next 10 subjects treated (first cohort).
 
Safety evaluation of the first 5 patients in this first cohort shows that inhibitor development is within the expected range.
 
The intention of this change in Amd 8 is to allow identification and screening of subjects while the safety evaluation in the first cohort of 10 subjects is completed.
 
Amd 8 also clarifies that patients may receive treatment other than BAY 81-8973 during the screening interval if medically indicated. If there are no safety concerns identified in the first cohort the patients may start treatment with study drug provided they still meet the protocol definition of MTP.
 
Screening therefore can continue to ensure continued enrollment in the study.

Section 4 Study design Section 6.1.1 Regular	Participation in the extension study is continued only until 100 ED are reached.	Kovaltry is now marketed, and therefore the extension study is offered until 100 ED and not until marketing authorization.

Section number and name	Description of change	Brief rationale
prophylaxis Section 6.8 Post-study therapy Section 7.1.1 Tabulated overview Section 7.1.2 Timing of assessments Section 7.1.2.10 Extension – final visit		

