A complete list of all participating centers and their investigators, as well as all required signature documents, will be maintained in the sponsor study file.

The global sponsor of this study is identified on the title page of this protocol.

If required by local law, local co-sponsors will be nominated; they will be identified on the respective country-specific signature pages.

4. Study design

Design overview

This is a phase-III multicenter, open-label uncontrolled study to demonstrate safety and efficacy of treatment with BAY 81-8973 for prophylaxis, breakthrough bleeds, and surgeries in children with severe hemophilia A. The study will be conducted worldwide.

The study is divided into two parts: Part A will investigate a total of 50 PTPs up to 12 years of age. Part B will include at least 25 PUPs, plus up to additional 25 PUPs/MTPs (as of Amd 6). All subjects will receive prophylactic administration of BAY 81-8973. Subjects in Part A will be treated with 25-50 IU/kg at least 2 times per week, or more frequently as needed for prophylaxis.

Treatment in Part B may begin with start of prophylaxis with 15-50 IU/kg (minimum dose 250 IU) at least one day a week, or with the subject's first bleeding event. The study drug will be used both for treatment of bleeding events and prevention of bleeds and with surgical procedures. Individual subject dose decisions are at the discretion of the investigator. (as of Amds 1 and 3)

Enrollment will be staggered. Part A will start after 20 adult/adolescent subjects have received 50 ED with BAY 81-8973 without safety concerns ***in previous studies with BAY 81-8973***. PTPs age ***6 to 12 years*** will begin enrollment first, followed by PTPs ***<6 years (as of Amd 3)***. Part B, for PUPs/MTPs ***(as of Amd 6)*** will begin enrollment after 20 children in Part A have had 50 ED. ***As of Amd 7, enrollment in Part B will be staggered. 10 patients will be enrolled, and will commence treatment for 20 ED.*** While safety assessment of the first cohort is ongoing, screening for the next sequence of 10 patients will continue. Treatment of next sequence/10 patients will start if no safety concerns are identified in the previous cohort following completion of 20 EDs. In the event patients would require FVIII treatment, they could still be eligible according to protocol definitions in case no more than 3 EDs of an alternative FVIII product has been administered.

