5.1 Eligibility

5.1.1 Inclusion criteria

In order to be included in the study, subjects must *have (as of Amd 1)* all of the following criteria upon evaluation at the Screening or Baseline visit:

Part A (as of Amd 1)

1. Male, age ≤ 12 years. ***Enrollment will begin with subjects 6-12 years before it is opened to all age groups. (as of Amd 1, Amd 3)***
2. Severe hemophilia A defined as $< 1\%$ FVIII concentration (FVIII:C) based on ***documented prior testing (as of Amd 1) or screening laboratory (Amd 3)***
3. ≥ 50 ED with any FVIII ***concentrate (as of Amd 1, Amd 3)***
4. No current evidence of inhibitor antibody measured using the Nijmegen-modified Bethesda assay [< 0.6 Bethesda units (BU)/mL] within 2-3 weeks ***of last FVIII (as of Amd 1) administration. PTPs (as of Amd 1) may not receive FVIII within 48 h prior to the collection of samples for inhibitor testing at the Screening visit. (as of Amd 1)***
5. No history of FVIII inhibitor formation. Documentation of negative result in medical records required. [Subjects with a maximum historical titer of 1.0 BU on no more than 1 occasion with the classical Bethesda assay but at least 3 successive negative (< 0.6 BU) results thereafter are eligible.]
6. Willingness and ability of subjects and/or parents to complete training in the use of the electronic patient diary (EPD) and to document ***infusions (as of Amd 1)*** during the study.
7. Written informed consent by parent/legal representative. Assent should be sought from subjects if appropriate

- **Part B (PUPs/MTPs):** *Enrollment s may start after safety is evaluated in 20 children in Part A with 50 ED (as of Amds 1 and 6).*

1. Male, <6 years (as of Amd 3)

2. Severe hemophilia A defined as < 1% FVIII:C based on *prior documented testing or confirmed on (as of Amd 1, Amd 3) screening* laboratory

3a. **PUPs:** No previous exposure to any FVIII *product (as of Amd 1)*

3b. **MTPs:** *Have no more than 3 EDs with any FVIII product and who have no current evidence of inhibitor antibody measured centrally using the Nijmegen-modified Bethesda assay [<0.2 Bethesda units (BU)/mL] at screening, with confirmation using local laboratory testing at baseline (<0.6 Bethesda unit [BU/mL]) (as of Amd 7). MTPs may not receive FVIII within 48 h prior to the collection of samples for inhibitor testing at the Screening and Baseline visits. (as of Amd 6 and Amd 7)*

3c. **MTPs:** *No history of FVIII inhibitor formation. (as of Amd 6)*

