01 FEB 2019

Version 7.0

Page: 35 of 262

- a CBC, chemistries; local labs as needed to reduce blood volume (Section 14.4)
- b In subjects > 7 kg at baseline visit. See recommendations for blood draws in subjects <10 kg (Section 14.4)
- c Measured at least 48 h after last dose of FVIII
- d Blood samples at the following time points: before, 20-30 min, 4 h, and 24 h post-infusion following a washout of 48 h after last dose of FVIII. Exact times need to be entered into CRF
- e Epitope mapping to be performed in combination with confirmatory retest for inhibitory antibodies (*as of Amd 4*)
- f The Final Visit can be performed as soon as a minimum of 50 ED is achieved, but no later than 2 weeks after achieving 50 ED. For the regular Extension Visit (performed every 6 months), a window of ± 2 weeks is allowed. The Extension Final Visit should take place no later than 2 weeks after 100 ED is achieved
- g The recommended biomarker investigation (pharmacogenetics) requires a separate signed informed consent (as of Amd 7). The single blood sample for this analysis can be taken at any visit except Screening, ideally at Visit 3 or whenever the subject's body weight/condition is suitable for an additional blood draw (as of Amd 4)
- h Inhibitor to be evaluated at screening (central laboratory testing), and at baseline (central and local laboratory testing), in MTPs only (ie, unnecessary to evaluate in PUPs) (as of Amd 6, include retention sample for inhibitor assessment by ELISA for MTPs). Study drug administration should start upon availability of result from local laboratory testing. (as of Amd 6 and Amd 7)
- j At the first extension visit 6 months after the start of the extension, and at any time in case of inhibitor development (as of Amd 6)
- k In case of MTPs, the screening visit should only take place after a washout period of at least 48 hours following any previous treatment with any FVIII replacement product (as of Amd 6).

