7.1.2 Timing of assessments

The main study consists of a Screening period *followed by at least 50 ED* per subject. *The Screening and Baseline visits may be combined to one visit for PUPs. There is no minimum interval between the Screening and Baseline visits for PUPs/MTPs (as of Amd 6) or PTPs. For PTPs, no longer than 8 weeks should pass between Screening and Baseline visits. (as of Amd 1)*

In Part A, PTPs, a minimum of 50 ED will be accumulated during a 6 month treatment period. Visits are scheduled at Month 1, Month 2 and Month 6. (as of Amd 1)

In Part B, the treatment period will be extended until 50 ED have been accumulated. The duration of Part B will vary and is dependent upon the frequency of prophylactic infusion and the number of bleeding events. Blood sampling for inhibitor testing is required every 3-5 ED up to 20 ED, and again at 50 ED. As most subjects will begin prophylaxis 1x week, study visits during the first 20 ED are expected to occur monthly. However, it is understood that bleeding events resulting in added doses, delayed start of prophylaxis after first bleeds, or missed infusions due to difficult i.v. access may result in some variation in the number of ED a subject has obtained at each visit or the exact interval between visits. Likewise, those subjects who receive more frequent infusions may require study visits more often than once a month. (as of Amd 1)

After completing Part A or B, all (as of Amd 1) subjects will be offered continued treatment in an extension study until a total number of at least 100 ED per subject are accumulated. Participation will require (as of Amd 1) additional visits every 6 months.

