7.1.2.1 Visit 1 – Screening

At the screening visit, the following procedures and assessments will be performed:

- Obtain written informed consent from the parents/legal representative. *Assent should be (as of Amd 1) obtained from subjects, depending on their age and intellectual status or according to local practice. (as of Amd 1)*
Note: No Screening procedures may be performed unless written informed consent (and assent, if applicable) has been obtained. (see Section 11.2)
- *Assignment (as of Amd 1) of a unique PID number (see Section 5.3)*
- Eligibility check
No subject may *receive treatment with study drug (as of Amd 1)* unless all *inclusion and exclusion criteria are met (as of Amd 1)* as given in Section 5.1. Confirmation of selection criteria may be based on medical records, but laboratory test results must confirm eligibility. The severity of *hemophilia may be based on documented FVIII level at diagnosis. (as of Amd 1)*
- Recording of *demographic data, medical and surgical history, and any adverse events (AEs) occurring after signing of informed consent. (as of Amd 3)*
- Recording of prior and concomitant medication *and Healthcare Resources Utilization Questionnaire. (Appendix 14.3). (as of Amd 1)*

- Measurement of vital signs: Systolic and diastolic blood pressure, heart rate, and body temperature. **Blood pressure may be deferred if appropriate cuff size or equipment is not available. (as of Amd 1)**
- Physical examination including measurement of body height/*length* and weight
- Blood samples for laboratory tests:
 - Complete blood count (CBC)
 - **Serum chemistry (sodium [Na], potassium [K], bicarbonate [CO], chloride [Cl], creatinine, alanine and aspartate aminotransferases [ALT, AST], total bilirubin. (See Section 14.4 for children <10 kg) (as of Amd 1)**
- **FVIII:C level for PUPs and MTPs, inhibitor testing (not required for PUPs but required for MTPs incl. a retention sample for ELISA) (as of Amds 1 and 6)**
- **Training on and dispensing (as of Amd 1) of the EPD. Note: the EPD may be given to the subjects to take home at any time between Screening and Baseline, but no entries are to be made before the first injection at Baseline (as of Amd 3).**

In case of MTPs, the screening visit should only take place after a washout period of at least 48 h following any previous treatment with any FVIII replacement product (as of Amd 6).

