5.1 Assignment of analysis sets

Final decisions regarding the assignment of subjects to analysis sets will be made during the review of study data and documented in the final list of important deviations, validity findings and assignment to analysis set(s) (see section 4.6).

The statistical analysis sets are defined as follows:

SAFety analysis set (SAF)

All subjects with at least one intake of study drug.

Subjects who were assigned to treatment but did not receive study medication will not be included in the SAF. As the number of these excluded subjects is anticipated to be negligible, if at all any exist in this design, an "all assigned treatment analysis set" will not be generated.

(modified) Intent To Treat Set (ITT)

All subjects of the SAF, who have infusion/bleeding data.

Per Protocol Set (PPS)

All ITT subjects who completed Part A and Part B of the study with no major protocol deviations.

Major protocol violations would be for example:

- Severe hemophilia A not confirmed
- Evidence of inhibitor antibody present at the time of screening.
- MTP has previously received more than 3 exposure days with any FVIII product, PUP has received any amount of FVIII
- In the prophylactic period here was/were at least
 - \circ one instance of >30 days between infusions
 - \circ two instances of >21 days between infusions
 - \circ three instances of >14 days between infusions

PharmacoKinetic Analysis Set (PK)

Statistical Analysis Plan PH-41074 Protocol No.: BAY 81-8973 / 13400

Page: 12 of 19:

Not applicable to this interim analysis, as it is not expected to get enough subjects for a reasonable analysis from part B. There will be an analysis of the pharmacokinetic data for the final CSR.

Listing Only Set (LOS)

Subjects who do not belong to SAF will not be included into statistical considerations. These subjects are classified as 'listing only set' (LOS). Number of screening failures and dropouts will be tabulated.

6. Statistical Methodology

The efficacy analyses will be based on the ITT and sensitivity analyses will be based on the PPS as appropriate.

The primary analysis population for the safety analysis will be the SAF.

6.1 **Population characteristics**

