6.4.1 Adverse events

The investigator has to record on the respective CRF pages all adverse events occurring in the period between the signing of the informed consent form and the end of the follow-up phase. The original terms used by investigators to report AEs via the CRFs will be coded using the Medical Dictionary for Regulatory Activities (MedDRA).

For each AE, the number and percentage of subjects who experienced at least 1 occurrence of the given event will be tabulated according to the affected primary system organ class (SOC) and preferred term (PT) by dose cohort and dose actually received. A total column will be included in all safety summaries.

Frequency tables, showing an overall summary of number of subjects with drug-related AEs, SAEs and AESIs will be given, and will include the following information:

- maximum intensity for any AE,
- AE related deaths,
- AE resulting in permanent discontinuation of study drug,
- treatment emergent AE.

AEs will be considered treatment-emergent if they begin after the first administration of study drug and they do not start after more than 7 days after the last administration. Determination of whether or not an event is treatment-emergent will be derived after the missing or incomplete AE start date is imputed. In case an adverse event starts on the day of first administration of study drug and the time of onset is not known, the event is considered to be not treatment emergent, if it is reported to occur before the first dose of study drug. In all other cases the event is considered to be treatment emergent. Inhibitors will be defined as treatment-emergent if they develop after first study drug application. Imputation rules for missing and incomplete AE start are described in section 4.3.

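### Part B children given another FVIII while waiting for their cohort can start study drug with a titre of 0.2 to <0.6 BU/mL, and the SAP has no rule to separate a resulting inhibitor from one arising on BAY 81-8973

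*Protocol*

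**What the plan says.** **Exposure while waiting.** Protocol Section 4 has the next 10 children screened while the current cohort completes 20 ED. If they need FVIII in that time, "they could still be eligible according to protocol definitions in case no more than 3 EDs of an alternative FVIII product has been administered". The Amendment 8 summary table shows that this is intended: "patients may receive treatment other than BAY 81-8973 during the screening interval if medically indicated". Inclusion criterion 3b for Part B counts ED with any FVIII product, so the limit of 3 is a total.

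**Inhibitor checks before study drug.** For MTPs, criterion 3b requires a central result below 0.2 BU/mL "at screening, with confirmation using local laboratory testing at baseline (<0.6 Bethesda unit [BU/mL"). Section 7.1.2.2 makes the local negative result the condition for giving study drug. Footnote h of Table 7-2b adds inhibitor testing at Screening "and at baseline (central and local laboratory testing), in MTPs only", but also ties the start of study drug to the local result. The MTP-specific withdrawal definition in Section 5.2.1 has a central limit at Screening and a local limit at Baseline. It sets no limit for the central Baseline sample.

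**PUPs.** Section 7.1.2.1 lists "inhibitor testing (not required for PUPs but required for MTPs incl. a retention sample for ELISA").

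**Interval.** Section 7.1.2 says "For PTPs, no longer than 8 weeks should pass between Screening and Baseline visits". It gives no maximum for Part B.

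**Analysis.** Part B SAP Section 6.4.1 states: "Inhibitors will be defined as treatment-emergent if they develop after first study drug application". Section 6.4.3 requires at least 0.6 BU centrally, with confirmation. Section 5.1 gives, as one major violation, "MTP has previously received more than 3 exposure days with any FVIII product, PUP has received any amount of FVIII", and as another an inhibitor present at screening; Baseline is not named.

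**The concern.** Protocol Section 8.3 promises the rate of inhibitor development associated with BAY 81-8973, and the SAP Supplement of 28 January 2020 lists inhibitor development as a secondary endpoint. Protocol Section 1 says that the early inhibitor risk in PUPs and MTPs exists with any FVIII product. The waiting period allows exposure to a different product, during the highest-risk exposure days, between the strict inhibitor test and the first study dose. No passage asks for the strict test to be repeated after that exposure, and the SAP attributes by timing alone. At stake is how far the Part B inhibitor rate can be read as a property of the study drug. There is also a practical question: whether sites can apply the eligibility text consistently to a PUP who is treated while waiting.

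**Working it through.** The plan gives no calculated figure to reproduce: Part B SAP Appendix 9.1 says that no formal sample size was determined. The check compares the rules and then sizes one case.

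**1. What happens to a titre raised by another product after the Screening sample.** Inputs: central limit 0.2 BU/mL at Screening and local limit 0.6 BU/mL at Baseline (Protocol 5.1.1, 7.5.3.4); positive test and event threshold 0.6 BU (Protocol 7.5.3.4, Part B SAP 6.4.3). Ratio of limits: 0.6 / 0.2 = 3.

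| Titre at Baseline (BU/mL) | Screening limit, if applied now | Local Baseline check | Consequence |
|---|---|---|---|
| <0.2 | passes | passes | starts study drug |
| 0.2 to <0.6 | fails | passes | starts study drug; counted as treatment-emergent if it later reaches 0.6 or more and is confirmed |
| 0.6 or more | fails | fails | withdrawn before study drug (Protocol 5.2.1) |

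Only the middle row leaks by rule. The central Baseline sample does not close it, because a value below 0.6 is not a positive test under Section 7.5.3.4 and no other limit is attached to that sample. Disagreement between local and central results, and sensitisation not yet measurable, add to it by an unknown amount.

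**2. The child screened as a PUP.**
- At Screening, no inhibitor test is required (7.1.2.1, 7.5.3.4).
- After treatment with another product he no longer meets criterion 3a and can qualify only as an MTP.
- Criterion 3b and Section 7.1.2.2 require a central Screening result for MTPs. Exclusion criterion 4 excludes anyone without a negative screening test, except PUPs.
- Section 4 says he could still be eligible. No passage says that he is re-screened.
- In the SAP he could be a PUP with a major violation or a valid MTP, because the time at which the status is fixed is not stated.

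**3. Length of the wait.** Protocol 7.1.2.8 expects 50 ED in 6 to 12 months after the start of prophylaxis for most children. Pro rata for 20 ED:
- 20/50 × 6 = 2.4 months; 2.4 × 52/12 = 10.4 weeks
- 20/50 × 12 = 4.8 months; 4.8 × 52/12 = 20.8 weeks

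That is about 10 to 21 weeks. Direct division agrees: 20 ED take 20 weeks at one infusion a week and 10 weeks at two. A child's own wait depends on when he is screened within that period. The PTP maximum, for comparison, is 8 weeks.

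**4. Size of one case.** The change in the observed rate is 1/n.
- n = 25: 1/25 = 4 percentage points
- n = 50: 1/50 = 2 percentage points

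For scale, assume 20 inhibitors in 50 children (40%, an illustration only). The exact 95% interval is 26.4% to 54.8%. With 21 in 50 (42%) it is 28.2% to 56.8%.

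**The case against.** **The leak is narrow.** The local Baseline limit equals the event threshold, so an inhibitor already at event level after another product should be caught. This stands and sets the scope of the point.

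**Section 4 does not waive the criteria.** It refers to protocol definitions, the Amendment 8 table requires that the child still meets the MTP definition, and eligibility is checked again at Baseline. A reader might infer that a treated PUP is admitted without any inhibitor test. The documents do not support that: the local Baseline test applies to MTPs, and exclusion criterion 4 read literally would exclude him. What remains is that Section 4 and the criteria point in different directions and re-screening is left unstated.

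**Reporting already exposes such cases.** Part B SAP Section 6.4.3 lists all inhibitor values for children with any positive result, Section 6.1.4 describes prior FVIII products in MTPs, and results are split by PUP, MTP and total. This helps a reader to examine individual cases. It gives no rule for interpreting them, and it does not identify comparable children without an inhibitor, who are needed for a denominator.

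**Admitting children with up to 3 ED of any FVIII is deliberate.** Agreed. Unmeasurable sensitisation exists in every MTP and no retest removes it. The point is only that a permitted exposure can follow the strict test.

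**Removing children with a Baseline titre of 0.2 or more from the count would be anti-conservative.** This stands. A possible carry-over does not show that the study drug played no part, so the full count must remain the main result.

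**Conclusion.** The point holds in limited form. On the current text, a post-exposure titre of 0.2 to <0.6 BU/mL, which would have failed Screening, can enter the rate reported for BAY 81-8973 if it later rises and is confirmed. The path for a PUP treated while waiting is not reconciled. Each such case is worth 4 points in 25 or 2 points in 50, which is small beside the sampling uncertainty at these sizes. The documents do not say how many children receive another FVIII while waiting, so the total effect cannot be estimated and may be nil. The waiting time of about 10 to 21 weeks assumes a constant pace to 50 ED.

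A reader might infer that carry-over inhibitors could also trigger the 50% suspension rule. Section 4 ties that rule to the first cohort, while the waiting provision concerns the cohorts that follow, so those children do not feed it directly. They can affect the overall Part B rate and the safety review of their own cohort. Nor do the documents show that the reported rate is in fact inflated; they show only that the plan could not tell. This is worth correcting mainly because the sample that would help is already drawn.

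**What to change.** 1. **Part B SAP, inhibitor analysis.** Keep the full inhibitor count as the main result. Add a pre-specified sensitivity analysis that excludes, from both numerator and denominator, children with a central Baseline titre of 0.2 BU/mL or more, or with another FVIII given between the Screening sample and the first study dose. List these children separately. In Section 5.1, extend the per-protocol example on inhibitors present at screening to cover the central Baseline result.
2. **Part B SAP, classification.** Fix PUP/MTP status at the first study dose, so that a child treated while waiting is reported in the MTP column and not as a PUP with a major violation.
3. **Protocol Sections 4, 5.1.1, 5.2.1, 7.1.2.2 and Table 7-2b footnote h.** Reconcile these passages so that the central inhibitor criterion is assessed on a sample taken after any FVIII given during the screening interval, including for a PUP who has become an MTP.

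Cost: items 1 and 2 are SAP wording and a little extra analysis, using the central Baseline sample that footnote h already requires in MTPs. Item 3 adds central turnaround time, or a re-screening sample, only in children treated while waiting.
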